7.2.2 Serious Adverse Events

Reporting of Serious Adverse Events

All serious adverse events occurring during clinical studies and within 30 days following the last study-related procedure must be reported by the investigator **within 24 hours** of their knowledge of the event by fax to the following address:

ZKS Cologne
[name]
Telefon: [name]
[contact]

The ZKS Cologne is responsible for SAE handling and documentation, SAE quality assurance, SAE- reporting to BfArM / CA / investigators and development of SAE database.

A serious adverse event form must also be completed within 24 hours of the awareness and forwarded to the above mentioned address. Each serious adverse event must be followed up until resolution or stabilization, by submission of updated reports. All serious adverse events that have not resolved by the end of the study, or that have not resolved upon discontinuation of the patient's participation in the study, must be followed until any of the following occurs:

- the event resolves
- the event stabilizes
- the event returns to baseline, if a baseline value is available
- the event can be attributed to agents other than the study drug or to factors unrelated to study conduct, or
- when it becomes unlikely that any additional information can be obtained (patient or health care practitioner refusal to provide additional information, lost to follow up after demonstration of due diligence with follow-up efforts)

Reporting of pregnancy

In the event of a pregnancy occurring in a patient or in a partner of a male patient after the first dose of the trial medication was applied has to be recorded on a pregnancy

form. This form must be reported by the investigator **within 24 hours** of their knowledge of the event by fax to the following address:

ZKS Cologne
[name]
Telefon: [name]
[contact] [name]

Monitoring of the patient will be continued until the conclusion of the pregnancy.

Development Safety Update Report – DSUR (former Annual Safety Report)

Once per year, the sponsor or PCI will supply a report on the safety of trial subjects with all available relevant information concerning patient safety during the reference period to the competent supreme federal authority and the competent authorities of all other member states of the EU or EEA where the trial is being conducted. This report will also be supplied to the responsible ethics committee.

The annual safety report will be compiled according to the corresponding ICH guideline E2F „Development Safety Update Report – DSUR“

The data-lock point for the patient data to be included and analyzed refers to the 11.06.2010 as day of clinical trial approval by the competent authority (BfArM).

The sponsor or PCI will supply the report within 60 days of one year after the reference date (data-lock point).

8. REFERENCE CENTERS

8.1 Neuropathology Reference Center

Before inclusion in the trial, the histological diagnosis of glioblastoma has to be confirmed by reference neuropathology. After obtaining informed consent for reference neuropathology and MGMT analysis a block of paraffin-embedded tissue has to be sent for reference neuropathology review to the following address.

[name]
Department of Neuropathology
University of Bonn Medical School
[name]
[contact]
[contact]

The result of reference histology is communicated to the local center within 10 days. Furthermore, the reference neuropathology center also sends part of the tissue to MDxHealth for MGMT promoter methylation status determination.

8.2 Central determination of MGMT status

MGMT promoter analysis is performed by

MDxHealth S.A. / HistoGeneX
Campus Middelheim
Laboratory building
[name]
[name]
BELGIUM
T: [name]
F: [name]

The test is performed on DNA from paraffin-embedded tissue using methylation-specific PCR. All analyses are performed according to internal SOPs. Tissue blocks are sent from the Department of Neuropathology to MDxHealth for MGMT testing. Sending of tissue blocks directly from the local centers to MDxHealth is not necessary. The results of the MGMT promoter analysis is communicated by email to the local treating center within 6 days after receiving the tissue block. In case of a non-methylated test result i.e. with a ratio of <2, the patient is not eligible for study treatment, cannot be randomized and is excluded from the the trial. Local testing of MGMT methylation status is discouraged.

8.3 Neuroradiology Reference Center

In case of progressive disease determined by the local neuroradiologist, contrast-enhanced MRIs showing progression as well as all previous MRIs have to be sent to the reference neuroradiologist for reference analysis:

[name]. [name]

Division of Neuroradiology, Department of Radiology, University of Bonn Medical Center

[name]

[contact], [contact],

Email: [contact]

The MRIs should be sent as electronic files on CD. The MRIs have to be sent blinded (only labelled with Pat.-ID) to ensure unbiased progression assessment. MRIs have to be accompanied by the Neuroradiology reference form (appendix 4). Results will be communicated within 5 working days. Study therapy is only discontinued if progressive disease is confirmed by reference neuroradiology. After the end of the study-specific follow-up of 3 years it is nevertheless mandatory to further follow-up the patient with contrast-enhanced MRI every 3 months until death.

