6. CLINICAL EVALUATION, LABORATORY TESTS, FOLLOW-UP

6.1 Study procedures

The attached Time and Events Schedule (Table 2) summarizes the frequency and timing of the various investigations and safety measurements. The neuroradiologic evaluation of response must be performed by contrast-enhanced MRI. A deviation of more than 5 days regarding the defined timepoints for each visit is regarded as a

protocol violation. This does not apply to the delay of chemotherapy courses due to prolonged toxicity in the previous course. The therapeutic options for patients who progress during study treatment are not determined by this protocol, but according to our previous experiences ([name] et al., 2006), intensified TMZ chemotherapy according to the one week on/off schedule (Wick et al., 2007) is recommended. To ensure reproducibility of MRI evaluation, all MRIs have to be reviewed by the reference neuroradiologist [name]. [name], Division of Neuroradiology, Department of Radiology, [name]. The MRIs have to be sent blinded (only labelled with Pat.-ID) to the reference neuroradiologist to ensure unbiased progression assessment.

In particular, the study visits include the following items:

- **Screening visit (week 1-3 after resection):**
 - Written informed consent for neuropathology reference testing and for MGMT testing

- **Baseline visit (week 3 to 5 after resection):**
 - Written informed consent for the trial
 - Inclusion/exclusion criteria (including MGMT and reference neuropathology test result)
 - Medical history and demographics
 - Vital signs
 - physical and neurological examination
 - concomitant medication
 - Karnofsky PS
 - Mini-Mental-Status evaluation and neurocognitive testing (NOA-07 test battery)
 - quality of life questionnaire
 - baseline contrast enhanced MRI scan (all post surgery MRIs not older than 3 weeks can be taken as baseline MRI (ideally early post surgery (72h))
 - ECG
 - spirometry
 - pregnancy test for women with reproductive potential
 - complete blood count and CRP
 - Blood sampling for translational studies

- serum chemistry and urine analysis
 - coagulation
 - Documentation of preexisting conditions in analogy to CTCAE
 - Randomisation
- **At the beginning of each course of CCNU/TMZ or TMZ:**

(Standard arm (TMZ): visit can be done within 5 days before start of cycle;
Experimental arm (CCNU/TMZ): visit has to be done on day of cycle start.

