- Since in some cases treated with CCNU/TMZ (Stuplich et al., in preparation), pseudoprogression may even ensue later than 12 weeks after the end of radiotherapy, i.e. up to the second scheduled clinical and MRI control examination 24 weeks after randomization, PD can only be diagnosed between week 12 after the end of radiotherapy and the scheduled clinical and MRI examination visit 24 weeks after randomization inclusively if progression according to the RANO criteria given above is confirmed in a scan 4 to 6 weeks after the scan suggesting progression. Therapy within the trial has to continue until confirmation of progression in the MRI scan 4 weeks later. If PD is confirmed, the earliest timepoint at which the criteria for PD had been fulfilled will be taken as the timepoint to calculate progression-free survival.

In any case PD is diagnosed in the local center according to the criteria given above, all MRIs starting with the baseline MRI have to be immediately sent to the reference neuroradiologist [name]. [name], Division of Neuroradiology, Department of Radiology, [name]. The MRIs have to be sent blinded (only labelled with Pat.-ID) to the reference neuroradiologist to ensure unbiased progression assessment. Therapy within the trial has to continue until confirmation of progression in the MRI scan by the reference neuroradiologist.

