9.2 Randomization

Randomization is carried out as central fax randomization. The randomization form (appendix 3) has to be faxed to the following address:

Clinical Study Core Unit, SZB
Institute of Clinical Chemistry and Chlinical Pharmacology
University of Bonn

[contact]

Phone (in case of any problems): [name]

Randomization is carried out according to a predefined randomization list for each center provided by the Institut für Medizinische Biometrie, Informatik und Epidemiologie (IMBIE), University of Bonn. Due to the different schedules for application of CCNU/TMZ (6 week courses) and standard TMZ (4-week courses), blinding of patients and of the treating physician is not possible. However, the reference neuroradiologist determining the day of progression on MRI will be blinded to the treatment protocol.

Randomization is stratified per participating center. Since age (<50 vs. ≥50 years), performance score (WHO performance score 0 vs. 1 or 2), extent of surgery (complete or partial resection vs. biopsy only) and mental state (MMSE ≥27 vs. <27) are strong prognostic factors in patients with newly diagnosed GBM (Gorlia et al., 2008), it would be desirable to also stratify randomization according to these parameters. With an average number of 10 patients recruited per center this does not appear to be feasible. Therefore, randomization is only stratified by center and the other prognostic factors are taken into account in the prespecified data analysis. The above mentioned prognostic factors have been implemented in 3 prognostic classes of GBM patients that have been developed by recursive partitioning analysis (RPA, Curran et al., 1993), validated in further trials (Scott et al., 1998) and further modified and validated using the data of the EORTC/NCIC trial (Mirmanoff et al., 2006) which defines the standard arm of CeTeG. The confirmatory analysis of the CeTeG trial will therefore analyze the primary endpoint OS not only stratified by center but also stratified by RPA class.

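### Section 6.1 requires blinded central review of every MRI, but Sections 6.2.1 and 8.3 provide for sending scans only after a local progression call, so detection of progression and part of best response rest on local readers

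*Protocol*

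**What the plan says.** Four sections of the protocol bear on this.

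- **Section 6.1** sets the scope without any condition: "all MRIs have to be reviewed by the reference neuroradiologist". On masking it adds: "The MRIs have to be sent blinded (only labelled with Pat.-ID) to the reference" reader.
- **Section 6.2.1** describes submission under a condition: "In any case PD is diagnosed in the local center according to the criteria given above". In that event, "all MRIs starting with the baseline MRI have to be immediately sent to the reference neuroradiologist".
- **Section 8.3**, which holds the address, the medium, the accompanying form and the reply time of five working days, has the same condition: "In case of progressive disease determined by the local neuroradiologist". The scans that show progression and every earlier one are then sent. It also says: "Study therapy is only discontinued if progressive disease is confirmed by reference neuroradiology".
- **Section 9.2** explains that patients and treating physicians cannot be blinded, and offers one safeguard: "the reference neuroradiologist determining the day of progression on MRI will be blinded to the treatment protocol".

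PFS and best response are secondary endpoints by modified RANO criteria (Sections 2.3 and 6.2.2). Neither definition names the reader.

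**The concern.** In an open-label trial, the blinded reference reader is the only reader whom the protocol states to be blinded. Section 6.1 gives that reader every scan. Sections 6.2.1 and 8.3 give that reader a patient's scans once the local center has diagnosed progressive disease (PD), and describe no route for scans of patients without such a diagnosis.

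If sites work from Section 8.3, the local reader decides whether the blinded reader ever sees a patient. Two things are then at stake. A progression that the site does not call is not detected centrally. Patients never called progressive, among whom durable responders will be found, have their best response read only locally.

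Section 6.2.1 itself supplies a reason why local calling could differ by arm. It warns that pseudoprogression may come later in some patients treated with CCNU/TMZ, so a local reader who knows the arm could be readier to discount enhancement in that arm.

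**Working it through.** No formula applies to the contradiction itself, so the check is a comparison of the sections.

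**1. Do the sections agree on which scans are sent?** They do not. Section 6.1 has no trigger. Sections 6.2.1 and 8.3 have one trigger, a local PD diagnosis. Both then ask for the earlier scans as well. That request is needed only if those scans had not already been sent, so it implies that routine submission was not in view.

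**2. What does each rule deliver?**

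| Situation | All MRIs reviewed (6.1) | Submission only at local PD (6.2.1, 8.3) |
|---|---|---|
| PD called locally too early | Read centrally | Read centrally; the call can be rejected |
| PD called locally on time | Read centrally | Read centrally; day of progression set by the blinded reader |
| PD called locally too late | Read centrally | All scans from baseline are read; the day can be set back |
| PD present, never called locally | Can be detected centrally | Never seen centrally |
| PD never present | Best response read centrally | Best response read locally only |

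The rules differ in substance only in the last two rows.

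**3. Which endpoints are touched?** Those with an MRI component: PFS, best response, and the PD component of time to treatment failure (Section 6.2.2). Section 6.2.2 defines PFS by documented progression and does not name death as an event. As worded, a progression that nobody documents gives no PFS event. Overall survival is death from any cause, so the 68 events and 80% power in Section 9.1 do not depend on who reads the scans.

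**4. How many patients could lack a central reading?** The protocol gives no expected number without a local PD call. As an illustration only, assume 15% to 30% of the 128 patients in the primary analysis:

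- 0.15 × 128 = 19.2, about 19 patients
- 0.30 × 128 = 38.4, about 38 patients

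Nothing in the protocol anchors this range.

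**5. Are the local readers unblinded?** No section says so outright. It is inferred from the open-label design and from Section 9.2, which names only the reference neuroradiologist as blinded.

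**The case against.** The strongest reply is that the sections can stand together. Section 6.1 would be the general rule, and Sections 6.2.1 and 8.3 the urgent procedure at suspected progression, with immediate dispatch, a quick answer and therapy continuing until confirmation. The word *only* does not stand in the submission rule of either section. On this reading nothing is contradicted, and a reader who infers that the protocol states two opposite rules goes too far.

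This stands in part. The intention may well have been both. But Section 8.3 is the section a site would use to send scans, and neither it nor any other section says when or how the remaining scans are sent. A site can comply fully with 8.3 and leave 6.1 unmet.

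A second reply is that local reading is itself constrained. Both arms share the 12-week MRI schedule, the numeric RANO thresholds and the special rules for early progression. That is true and limits the room for bias, but it does not replace a blinded reading.

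A third reply is that the choice of reading for analysis may be set in the statistical analysis plan, which is not shown. That may be so for the analysis. Which scans the sites send is a site procedure, and the protocol has to settle it.

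**Conclusion.** The point holds for the detection of progression and for best response. If Section 8.3 is what sites follow, progression never called locally escapes the blinded reader, and patients never called progressive have no blinded response reading. The number affected cannot be derived from the protocol; the 19 to 38 patients above rest on an assumed proportion. The direction of any bias is also unknown, and its presence depends on local readers knowing the arm, which is inferred.

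A reader might infer more: that local delay or eagerness passes directly into PFS, for instance that one late call moves progression by a full 12-week interval. The documents do not support this. After any local call the blinded reader receives every scan from baseline, confirms or rejects PD, and determines the day of progression. The date of a called progression is therefore largely protected, and a shift remains only where a late call is not re-dated centrally. Nor can such a shift be scaled against the 7.9-month median PFS in Section 1.1, which is quoted there without selection by MGMT status, whereas this trial enrols only patients with a methylated promoter.

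The primary endpoint is untouched. This is a correction worth making for the MRI-based secondary endpoints.

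**What to change.** Reconcile Sections 6.2.1 and 8.3 with Section 6.1:

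- Keep immediate submission at a local PD call as the real-time step, unchanged.
- Add that all remaining study MRIs, scheduled and unscheduled, of all patients, including those without a local PD call, are sent under the patient ID alone and read by the reference neuroradiologist already named, blinded to arm, before database lock.
- State that this central reading supplies the MRI component of PFS and best response, to be combined with the neurological and steroid criteria of the modified RANO definition. Scans alone do not decide these endpoints.

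The blinding needed is to arm. Blinding the same reader to the local call is not asked for: the urgent cases reach that reader because of the local call.

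The cost is a change of wording, the dispatch of the remaining scans, and reading time before lock. Section 6.1 already implies this work, the scans are already scheduled every 12 weeks, and Section 9.3 starts the analysis only 36 months after the last inclusion. If the sponsor in fact intends review only after a local PD call, Section 6.1 has to be corrected instead, and the dependence on local readers stated as a limitation.

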9. STATISTICS

9.1 Sample Size Consideration

The trial has to accrue 128 evaluable patients (64 evaluable patients per arm). The sample size calculation is based on the following facts:

- The EORTC/NCIC trial (Hegi et al., 2005) showed that patients with a methylated MGMT promoter treated with standard TMZ chemotherapy (identical regarding inclusion criteria and therapy to the patients in the standard arm of the proposed CeTeG trial) have a 2 year overall survival rate of 48.9%
- The UKT-03 trial ([name] et al., 2006; Glas et al., 2009) showed that patients with a methylated MGMT promoter treated with CCNU/TMZ (identical regarding inclusion criteria and therapy to the patients in the experimental arm of the proposed CeTeG trial) have a 2 year overall survival rate of 75%.

Overall survival (OS) is the primary outcome parameter on which power and sample size calculations for the CeTeG trial are based. It is expected that in the CeTeG trial the experimental CCNU/TMZ therapy can increase the 2 year survival rate from 48.9% in the standard arm to 70% in the experimental arm (slightly less than the 75% observed in the previous phase II trial). Assuming this increase in overall and assuming exponentially distributed survival times, a constant recruitment of 64 patients per treatment group over two years with a follow-up of additional three years will result in a power of 80% for the intended two-sided log-rank test (level of 5%). This timepoint has been delayed from 24 months in previous versions of the protocol to 36 months. The reasons for this delay were as follows:

The assumptions for the initial planning of the trial match to event (death) rates of 0.356 and 0.176 events per patient year and result in an expected number of 68 events after two years of recruitment and two years of follow-up. . A blinded analysis of the overall survival time 14 months after last-patient-in (36 months after first-patient-in) showed that there is an overall mean risk for the event “death” of 0.1994/patient year due to an unexpected low number of events at this time and indicating a low number of events at the end of the intended follow-up-time which might result in a power lower as expected. With the observed actual event rate and an assumed OR of 2 as planned, the 68 events required for an analysis with a sufficient power of 80% can be reached by a prolongation of the follow-up time to April 2017, i.e. 36 months after last-patient-in. The sample size calculation was performed using the “PS” power and sample size program (Dupont and Plummer, 1997) and additional simulation analysis. Assuming that 6% of patients may not be analyzable for the primary endpoint OS due to non-compliance or loss to follow-up before the start of chemotherapy, additional 8 patients adding up to a total of 136 MGMT-methylated patients have to be randomized for the trial. Dropout patients and patients lost for follow-up after the start of chemotherapy will be evaluated as observations censored at the time of dropout. The figure of approx. 6% patients who may be non-compliant and/or lost for follow-up for the ITT evaluation of the primary endpoint may be overestimated. In the previous bicentric phase II trial with CCNU/TMZ ([name] et al., 2006; Glas et al., 2009), none of the 31 patients included was lost for follow-up or non-compliant. This corresponds to experiences of most centers with other trials for untreated GBM such as the so far not published phase II cilengitide trial. In experienced neurooncological centers as the ones taking part in the CeTeG trial, the lost-to-follow-up rate is very low. The long-term analysis of the EORTC/NCIC trial

defining the CeTeG standard arm shows that only 9 of the 573 patients (1.6%) randomized refused further involvement in the trial (Stupp et al., 2009). The situation in the EORTC/NCIC trial can well be transferred to the situation in the CeTeG trial since some of the centers in the CeTeG trial have already participated in the EORTC/NCIC trial. To have nevertheless an adequate safety margin it appears to be prudent to calculate with a higher, i.e. 6% non-compliance rate until the start of chemotherapy. Since the ITT evaluation comprises all patients that have receive a first dose of chemotherapy (labelled as censored observations) the expectedly low rate of malcompliance and loss for follow-up rate after the start of chemotherapy is not important for the adequate analysis of the trial.

A methylated MGMT status and confirmation of GBM histology by the neuropathology reference center are the major inclusion criteria which are not yet available during the screening visit but which have to be fulfilled for randomization. Thus, it has to be taken into account that also a few patients with a non-methylated MGMT promoter and mMGMT patients with local GBM histology but reference diagnoses other than GBM (reference neuropathology is performed after MGMT testing) are screened for the trial. According to the German Neuropathology Reference Center at the Department of Neuropathology, University of Bonn, which is also serving as reference center for this trial, approx. 7% of the local diagnoses of GBM cannot be confirmed by the reference center ([name], personal communication). Thus, if 136 patients have to be randomized, reference neuropathology has to be performed on 145 patients. Assuming that only 45% of newly diagnosed GBM patients have a mMGMT tumor (Hegi et al., 2005), for 145 patients evaluated in reference pathology, 322 patients with newly diagnosed GBM and matching inclusion/exclusion criteria have to be screened and analyzed for MGMT promoter methylation status (“patients screened for eligibility”).

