Study Design / Development phase	Prospective, open-label, randomized, multicenter phase III study
Objective	To analyze whether combined CCNU/TMZ therapy is superior to standard TMZ regarding efficacy as measured by overall survival
Number of subjects	To be assessed for eligibility n = 658 To be allocated to trial n = 141 To be analyzed n = 128 (ITT)
Investigational products	TMZ (Temozolomide) CCNU (Lomustine)
Treatment plan	After central neuropathology confirmation of glioblastoma and confirmation of a methylated MGMT status, patients are randomized into 2 arms: Experimental arm (CCNU/TMZ arm): 60 Gy standard radiotherapy (RT, 30 x 2 Gy) Six 42-day courses of oral CCNU 100 mg/m ² (day 1) and oral TMZ 100 mg/m ² (day 2-6), first CCNU application starting with the first day of RT CCNU/TMZ and radiotherapy start 2-5 weeks after diagnosis (day of surgery for glioblastoma (GBM)). In courses 2-6, TMZ dose are adjusted according to the hematotoxicity observed in the previous course and can be increased stepwise

	
up to 200 mg/m²/day
 
Standard arm (TMZ arm): 60 Gy standard radiotherapy (RT, 30 x 2 Gy) and concomitant TMZ therapy (daily TMZ 75 mg/m²) starting with the first day of radiotherapy Six 28-day courses of TMZ (day 1-5) starting 4 weeks after completion of radiotherapy. In the first course TMZ is given at a dose of 150 mg/m²/day, in case no toxicity is observed, the 2nd course is applied at a daily dose of 200 mg/m² Concomitant TMZ and radiotherapy start 2-5 weeks after diagnosis
 
Follow-up per patient: Each patient will be followed until at least 36 months after randomization. Follow-up of all patients ends 36 months after the inclusion of the last patient. All patients in the trial are followed until this time point.
 
Duration of intervention per patient: Experimental arm: 6 courses CCNU/TMZ à 42 days = 9 months Standard arm: 6 weeks radiotherapy + concomitant TMZ, 4 weeks treatment pause, 6 courses of TMZ à 28 days = 8.5 months

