3.6 Patients Replacement

According to the patient number calculation, 136 patients have to be allocated and 128 of these allocated patients are expected to form the intention-to-treat (ITT) population which included all patients who are included in the trial and have received their first dose of chemotherapy. This implies that about 6% of the patients (n=8) included in the trial are anticipated to be drop-outs before starting chemotherapy. These drop-out patients are not replaced.

Any patient dropping out after receiving his first dose of chemotherapy is part of the ITT population and is not replaced.

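### Section 9.1 ties its 80% power at three years of follow-up to survival rates that give 85–88%, calls a hazard ratio an odds ratio, and disagrees with the synopsis on numbers and accrual

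*Protocol*

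**What the plan says.** Section 9.1 expects the experimental regimen to "increase the 2 year survival rate from 48.9% in the standard arm to 70% in the experimental arm", with exponential survival. On that basis constant "recruitment of 64 patients per treatment group over two years with a follow-up of additional three years will result in a power of 80" percent "for the intended two-sided log-rank test (level of 5" percent). It adds that the time point was moved from 24 to 36 months and then gives the reasons.

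The initial assumptions are said to match death rates of 0.356 and 0.176 per patient-year and to "result in an expected number of 68 events after two years of recruitment and two years of follow-up". A blinded look, "14 months after last-patient-in (36 months after first-patient-in"), found 0.1994 deaths per patient-year overall. "With the observed actual event rate and an assumed OR of 2 as planned", the 68 deaths needed for 80% power are said to be reached 36 months after the last patient enters.

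On numbers, section 3.6 says "136 patients have to be allocated and 128 of these allocated patients" should form the ITT population. Section 9.1 also gives 136, from a 6% loss before chemotherapy, and 322 to be screened. The synopsis says "To be allocated to trial n = 141", with 658 assessed for eligibility. For accrual, section 9.1 and the synopsis text give two years. The synopsis line for first to last patient in prints 33 and 35 months side by side.

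**The concern.** One pair of survival rates, one sample size and one accrual period cannot give 80% power at both two and three years of follow-up. Section 9.1 links the 68 deaths to the first and the 80% to the second. The follow-up length in the power sentence appears to have been updated while the survival rates and the power stayed as they were.

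At stake is whether the sample size statement for the primary endpoint can be reproduced, and whether a reader can tell which event rate and which effect size justify the extra year. The effect label matters for the same reason: a log-rank calculation runs on a hazard ratio, and the odds ratio implied by this plan is a different number. The conflicting counts leave the enrollment target and the screening load unsettled between the synopsis and the body.

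**Working it through.** **Inputs (section 9.1).** Two-year survival 48.9% and 70%; exponential survival; 64 per arm; uniform accrual A = 2 years; minimum follow-up F = 2 or 3 years; two-sided 5% log-rank test; blinded pooled rate 0.1994 per year.

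**Hazards.** h = −ln(S)/2, so −ln(0.489)/2 = 0.3577 and −ln(0.70)/2 = 0.1783, ratio 2.006. The printed rates give 0.356/0.176 = 2.02.

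**Formulas.**
- P(death) = 1 − [exp(−hF) − exp(−h(A+F))]/(hA); deaths d = 64 × (sum over both arms)
- Schoenfeld power = Φ(√(d/4) × ln HR − 1.96)
- Freedman power = Φ(√d × (HR − 1)/(HR + 1) − 1.96)

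**The plan's own figure, 2 + 2 years.** P = 0.6507 and 0.4112; d = 64 × 1.0619 = 68.0. Schoenfeld: Φ(2.87 − 1.96) = 81.8%. Freedman: Φ(2.76 − 1.96) = 78.8%. The 68 deaths and the 80% reproduce here.

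**The sentence as written, 2 + 3 years.** P = 0.7557 and 0.5074; d = 64 × 1.2631 = 80.8. Schoenfeld: Φ(3.13 − 1.96) = 87.9%. Freedman: Φ(3.01 − 1.96) = 85.3%. The printed rates 0.356 and 0.176 give 80.4 deaths and 85.9–88.5%.

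**The blinded rate, 2 + 3 years.** With a hazard ratio of 2 and an arm average of 0.1994, the hazards are 0.1994 × 4/3 = 0.2659 and 0.1994 × 2/3 = 0.1329. P = 0.6507 and 0.4107; d = 64 × 1.0614 = 67.9. Schoenfeld: Φ(2.86 − 1.96) = 81.5%. Freedman: Φ(2.75 − 1.96) = 78.4%.

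| Inputs | Accrual + follow-up (years) | Deaths | Freedman | Schoenfeld | Simulated log-rank |
|---|---|---|---|---|---|
| 48.9% vs 70% | 2 + 2 | 68.0 | 78.8% | 81.8% | 81.1% |
| 48.9% vs 70% | 2 + 3 | 80.8 | 85.3% | 87.9% | 87.1% |
| 0.1994 pooled, HR 2 | 2 + 3 | 67.9 | 78.4% | 81.5% | 81.5% |

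**Effect measure.** The planned two-year odds ratio is (0.70/0.30)/(0.489/0.511) = 2.44. The planned quantity that equals 2 is the hazard ratio.

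**Counts.** 128/0.94 = 136.2, which agrees with 136 and the stated 6% loss, and 145/0.45 = 322 agrees with section 9.1. The synopsis figures do not follow from section 9.1. Starting from 141 and applying its 7% unconfirmed histology and 45% methylated gives 141/0.93/0.45 ≈ 337, not 658.

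**Accrual.** The 71-month total in the synopsis text, less 6 months of preparation, 36 of follow-up and 6 of analysis, leaves 23 months. That fits two years, not 33 or 35 months. The effect on power is small: at the blinded rate with a hazard ratio of 2 and three years of follow-up, 33 months gives 71.6 deaths (80.5–83.5%) and 35 months gives 72.3 deaths (80.9–83.8%).

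**The case against.** The strongest defense is that section 9.1 explains itself. Directly after the power sentence it says that follow-up was lengthened and gives the initial rates, the 68 deaths at 2 + 2 years, the lower blinded rate and the new date for 68 deaths. That sequence reproduces, so a careful reader can recover the basis for the extension. The slip is also conservative. Section 9.3 starts the analysis at a calendar time, 36 months after the last patient enters, so no figure here changes conduct. All of this stands and limits the weight of the point. It does not make the power sentence correct, and it does not touch the label or the synopsis counts.

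Some stronger readings are tempting but are not supported:
- **The blinded data refute the planned rates.** Section 9.1 gives no death count. Assuming 128 patients, 22 months of accrual and a hazard ratio of 2, 0.1994 corresponds to about 43 deaths in 216 patient-years, with a 95% interval of about 0.1994 × exp(±1.96/√43) = 0.15 to 0.27. The planned rates at that look give (0.5168 + 0.3072)/(1.445 + 1.723) = 0.26 (deaths over patient-years per patient, summed over arms), inside the interval.
- **The trial is really powered for an odds ratio of 2.** The text says as planned, and the planned rates beside it have a ratio of 2.02. This is a wrong label, not a second target.
- **Accrual of 22 months contradicts two years.** The 22 months (36 − 14) reflect actual recruitment; two years is the plan.
- **The plan assumes two different loss rates.** Only 6% is stated. The larger loss implied by 141 is the same count mismatch seen again.

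The doubled synopsis figures may be strike-through lost in conversion, so the doubling itself is no error. Either value still disagrees with two years.

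**Conclusion.** The point holds as a defect of statement. With the inputs it names, section 9.1 should give about 81 deaths and 85–88% power, not 80%. The stated figure belongs to two years of follow-up at those rates, or to the blinded rate with a hazard ratio of 2 at three years. The effect is mislabeled as an OR, and the synopsis disagrees with the body on patients allocated (141 against 136), patients screened (658 against 322) and accrual time.

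A reader might infer that the trial is underpowered. It is not shown to be: the sentence understates power under its own rates, and about 68 deaths with roughly 78–82% power at 36 months is supported on the revised basis. The figures assume exponential survival, uniform accrual, 128 analyzed patients, no other loss and an unstratified log-rank test. The planned test is stratified by center and RPA class, and that effect is not quantified here.

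**What to change.** Reword section 9.1 so that each power figure stands with its own inputs:
- 48.9% versus 70% with two years of accrual and two of follow-up gave about 68 deaths and about 80% power (kept as the history of the plan).
- The blinded pooled rate of 0.1994 per patient-year with a hazard ratio of 2 gives about 68 deaths and about 80% power at 36 months after the last patient enters.
- The original rates would give 85–88% power at 36 months.

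Replace OR with hazard ratio. Give one number to be randomized, one to be screened and one accrual time, the same in the synopsis, section 3.6 and section 9.1. On the stated 6% loss, 136 is the number that follows from 128.

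The cost is wording only. Enrollment, follow-up and the analysis do not change.
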